6.7. COMMON CALCULATIONS

The following common calculations will be applicable:

- For quantitative measurements, change from baseline at visit X will be calculated as:

$$\text{Change from baseline} = \text{result value at visit X} - \text{baseline value}$$

- For quantitative measurements, percent change from baseline at visit X will be calculated as:

$$\% \text{ Change from baseline} = 100\% \times \frac{\text{result value at visit X} - \text{baseline value}}{\text{baseline value}}$$

- The duration of the bilateral insertion/sham procedure in minutes will be calculated as the difference between the beginning time of the first study article preparation and the time of completion of the procedure, as captured on the LYR-210 Administration/Sham Procedure eCRF:

$$\begin{aligned} & \text{Duration of insertion or sham procedure in minutes} \\ & = \text{time of completion of procedure} - \text{beginning time of article preparation} \end{aligned}$$

- The duration of the depot/sham removal procedure in minutes will be calculated as the difference between the start and end times of the removal procedure, as captured on the End of Treatment eCRF:

$$\begin{aligned} & \textit{Duration of removal procedure in minutes} \\ & = \textit{end time of removal procedure} - \textit{start time of procedure} \end{aligned}$$

7. STATISTICAL CONSIDERATIONS

7.1. SAMPLE SIZE

Per the null and alternative hypotheses described in Section 7.8 and under the assumption that $\mu_C = -1.30$ and $\mu_{L_{2500}}$ and/or $\mu_{L_{7500}} = -3.00$ (conservatively set, based on the mean of this endpoint for LYR-210 in Phase I study, and approximately 130% larger decrease than the assumed control mean of -1.30) and that the true standard deviation (SD) of the primary endpoint within each treatment group is at most 2.4, then an evaluable sample size of 63 subjects (21 per treatment group) yields 73% power to reject at least one null hypothesis in favor of the alternative at a one-sided 0.05 level of significance. An additional 6-9 subjects will be enrolled to account for potential subject dropout.

7.2. SUMMARY STATISTICS

For continuous data, descriptive statistics (i.e., n [number of subjects with available data], mean, SD, median, minimum, and maximum values) will be presented by treatment group and visit, when applicable.

For categorical data, the number and percentages of subjects in each category will be presented by treatment group and visit, when applicable.

7.3. MISSING DATA

Missing efficacy data for the primary and secondary endpoints will be handled as described in Sections 15.1.2 and 15.2.3, respectively. No missing data methods will apply for exploratory endpoints.

Missing safety data will not be imputed.

7.4. ADJUSTMENTS FOR COVARIATES AND FACTORS TO BE INCLUDED IN ANALYSES

The following covariates and factors will be used in the primary and secondary analyses when an analysis of

covariance (ANCOVA) is performed. For details of their inclusion in the models please refer to Section 15.

- Covariates:
 - Baseline value of the concerned endpoint
- Factors:
 - Treatment group (fixed effect)
 - Randomization stratification variables
 - Nasal allergy (Yes/No)
 - Nasal polyps (Yes/No)

7.5. MULTICENTER STUDIES

This study will be conducted by multiple investigators at multiple centers internationally. Randomization to treatment arms is not stratified by country, region or center. Approximately 25 sites will participate in the study. Data from all centers will be pooled together in the analyses.

In order to assess the treatment effect across regions, descriptive statistics for the primary endpoint will be presented for each treatment for each region. Geographic region will be categorized as follows:

Geographic Region	Identifier Code in Subject ID
Australasia	Australia (036) and New Zealand (554)
Europe	Czech (203) and Poland (616)

In addition, an exploratory ANCOVA on the primary endpoint will include region and treatment-by-region interaction as factors (fixed effects). Please refer to Section 15.1.5 for more details. It is to be noted that should data be too sparse for at least one treatment group in at least one region (i.e. less than 5 ITT subjects for at least one treatment group in at least one region), only descriptive statistics by region will be provided.

7.6. EXAMINATION OF SUBGROUPS

Subgroup analyses will be conducted as stated in the exploratory analysis sections to assess the consistency of treatment difference across the subgroups. It should be noted that the study was not designed to detect treatment differences with high statistical power within subgroups.

The following subgroups will be relevant to the exploratory analysis for this study:

- Nasal allergy:
 - Yes.
 - No.
- Nasal polyps:
 - Yes.
 - No.
- Baseline CS7DA4S:
 - Below median.
 - At or above median.
- Sex:
 - Male.
 - Female.
- Age:
 - Below median.
 - At or above median.
- Region:
 - See Section [7.5](#).
- Baseline Total Bilateral Zinreich Score as assessed by MRI:
 - Below median.
 - At or above median.

In the subgroups above, median is referencing the overall median for the ITT analysis set, regardless of the treatment group.

If data are too sparse for at least one treatment group in a subgroup (i.e. less than 5 ITT subjects for at least one

treatment group in a subgroup), only descriptive statistics by treatment group will be provided for that subgroup. That is, no statistical inferences will be performed for that subgroup.

7.7. STATISTICAL TESTS

The default significance level will be 5% and all tests will be one-sided, unless otherwise specified in the description of the analyses. Two-sided 90% CIs will be presented for all outputs were relevant.

7.8. MULTIPLE COMPARISONS/MULTIPLICITY

The primary objective of this study is to test the following null and alternative hypotheses:

$$H_0: \mu_{L_{2500}} = \mu_C \text{ vs. } H_1: \mu_{L_{2500}} < \mu_C$$

$$H_0: \mu_{L_{7500}} = \mu_C \text{ vs. } H_1: \mu_{L_{7500}} < \mu_C$$

where $\mu_{L_{2500}}$, $\mu_{L_{7500}}$ and μ_C are the true mean values of the CFBL in the CS7DA4S score at Week 4 for the LYR-210 2500 μg , LYR-210 7500 μg , and control (Sham procedure) treatment groups, respectively.

Given the exploratory nature of the study, no adjustment to the overall alpha-level of the study will be made for multiple comparisons and multiplicity. That is, only nominal p-values will be provided for the primary efficacy endpoint, key secondary endpoints, non-key secondary endpoints, and exploratory efficacy endpoints.

7.9. SOFTWARE VERSION

All analyses will be conducted using SAS version 9.4 or higher.

8. OUTPUT PRESENTATIONS

[APPENDIX 1](#) shows conventions for presentation of data in outputs.

The table, figure and listing (TFL) shells provided with this SAP describe the presentations for this study and therefore the format and content of the summary tables, figures, and listings to be provided by ██████████ Biostatistics.

9. DISPOSITION AND WITHDRAWALS

All subjects who provide informed consent will be accounted for in this study.

Subject disposition will be summarized for the CONS analysis set overall and by randomized treatment group. The number of patients screened, and screen failed will be presented. The number and percentage of subjects randomized into the study, treated and had a treatment attempt, who completed/discontinued early from the study treatment (including reasons for discontinuation) and who completed/discontinued early from the study (including reasons for discontinuation) will be presented.

Subjects' randomization details, end of treatment status, removal procedure and end of study status will be listed.

Analysis set assignment will be summarized for the CONS analysis set overall and by randomized treatment. The reasons for exclusion from each analysis set will be listed and summarized overall and by randomized treatment group.

9.1. PROTOCOL DEVIATIONS

All protocol deviations will be recorded in the CTMS log for the duration of the study. Deviations will be assessed and categorized as critical, major or minor. Site level IDs will be replicated for all subjects at that site and presented in the summary outputs as subject level deviations.

A table will be produced summarizing the type and severity of each protocol deviation overall and by randomized treatment group for the ITT analysis set. The summary will be presented on the number and percentage of subjects with each type and severity of deviation. All reported PDs will be listed.

10. DEMOGRAPHIC AND OTHER BASELINE CHARACTERISTICS

Demographic data and other baseline characteristics will be listed and summarized by treatment group for the ITT analysis set. No statistical testing will be carried out for demographic or other baseline characteristics.

The following demographic and other baseline subject characteristics will be reported for this study:

- Age (years) – as reported on the Demography eCRF page
- Sex (Female/Male) and female childbearing potential
- Race (American Indian or Alaska Native, Asian, Black or African American, Native Hawaiian or Other Pacific Islanders, White, Other)
- Ethnicity (Hispanic or Latino, Not Hispanic or Latino, Not Reported, Unknown)
- Region (Australasia, Europe)

- Height (cm)
- Weight (kg) at Baseline
- BMI (kg/m²) at Baseline – refer to Section 10.1
- The baseline symptom scores for the 4 individual cardinal CS symptoms and total CS7DA4S
- Time since CS onset
- Characteristics of subjects' CS disease relevant medical history, as captured on the Chronic Sinusitis disease relevant medical history eCRF, including chronic sinusitis, asthma, perennial allergic rhinitis, seasonal allergic rhinitis, sensitivity to non-steroidal anti-inflammatory drugs (NSAID), chronic obstructive pulmonary disease (COPD) and smoking status.
- Characteristics of CS disease relevant surgical history
- Time since disease relevant surgery.

10.1. DERIVATIONS

- Time since onset of CS:

$$\text{Time since CS onset (years)} = \frac{\text{date of informed consent} - \text{date of CS onset}}{365.25}$$

- Time since disease relevant surgery will be calculated as:

$$\text{Time since surgery (years)} = \frac{\text{date of informed consent} - \text{date of surgery}}{365.25}$$

For all the above calculations if the start and/or end date is/are partial, only the available segment(s) of the date that appear in both dates will be used in the calculation. For example, if only the year of the start date is available, and the month and year of the end date are available, the calculation will only be between the start and end years. If only month level is used the calculation should be divided by 12 to obtain the duration in years. No division will occur if only year is available.

- BMI (kg/m²) will be derived as follows:

$$BMI = \frac{\text{Weight in kg}}{(\text{Height in m})^2}$$

11. SURGICAL AND MEDICAL HISTORY

CS disease relevant medical/surgical history will be listed and summarized for the ITT analysis set as per Section 10. All other Medical and Surgical History will be listed only for the SAF analysis set.

Medical and Surgical History will be coded using Medical Dictionary for Regulatory Activities (MedDRA) version 23.0 or later.

12. MEDICATIONS

Medications other than CS medical treatment history (see Section 10) will be coded World Health Organization Drug Dictionary (WHO-DD) version March 2020 or later. No Anatomical Therapeutic Class (ATC) coding will be performed for this study.

See APPENDIX 2 for handling of partial dates for medications. In the case where it is not possible to define a medication as prior, concomitant, or post-treatment, the medication will be classified by the worst case; i.e. concomitant.

- ‘Prior’ medications are medications which started and stopped prior to the bilateral insertion/Sham procedure or treatment attempt.
- ‘Concomitant’ medications are medications which:
 - started prior to the bilateral insertion/Sham procedure/treatment attempt AND were ongoing or ended after the bilateral insertion/Sham procedure/treatment attempt;
 - started on the day of the bilateral insertion/Sham procedure/treatment attempt;
 - started after the bilateral insertion/Sham procedure/treatment attempt but before or on the removal/Sham removal + 28 days.
- ‘Post-treatment’ medications are medications which started after the bilateral removal/Sham procedure + 28 days.

Prior, Concomitant and Post Medications will be listed by WHO drug name concatenated with base name for the SAF analysis set.

13. STUDY TREATMENT EXPOSURE

Descriptive statistics of exposure to study treatment in weeks will be presented for each treatment group in the ITT

analysis set.

The duration of exposure will be based on the difference of the date of successful bilateral insertion procedure taken from the LYR-210 Administration/Sham Procedure eCRF and the relevant event date. The event date is defined by whichever of the following events occurs first for a subject:

- Date of end of treatment (date collected on the End of Treatment eCRF) for subjects completing or early discontinuing treatment
- Depot dislodgement (date collected by the randomization vendor). If only one depot was dislodged, this will not be considered as an event. If both depots dislodged, but not simultaneously, the date of the second dislodgement will be considered as the event date.

Duration of exposure will not be calculated for subjects with an unsuccessful treatment attempt.

13.1. DERIVATIONS

Duration of exposure is calculated as below and will be rounded to 1 decimal place:

$$\text{Duration of exposure (weeks)} = \frac{\text{date of event} - \text{date of insertion procedure} + 1}{7}$$

14. SALINE IRRIGATION COMPLIANCE

Compliance to daily saline irrigation will be presented descriptively by treatment group for the ITT analysis sets as collected in the ePRO.

Compliance will be presented as a percentage of the days saline irrigation was done relative to the duration of the washout and treatment periods (days). The washout period information is collected on the Washout Period eCRF.

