**Figure 1: Study Design Schematic**

#### **4.1.1 Screening Stage**

After providing written informed consent, subjects who are qualified to participate in this study will have an initial Screening visit. Immediately following the initial Screening visit, subjects will undergo a minimum of 2-week but a maximum of 4-week washout period. During this washout period, subjects will receive no active treatment for CS but are recommended to start daily saline irrigation twice a day. Subjects will be provided with saline and instructions for daily intranasal saline irrigations while participating in the study.

Medications that are prohibited during the washout period (and during the study) are listed in Section 6.4.2. Beginning at least 7 days prior to Day 1 visit, subjects will record the severity of the 4 cardinal symptoms of CS and the use of saline irrigation each day in the morning on the electronic subject reported outcomes (ePRO) questionnaire.

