#### **6.4.3 Permitted Concomitant Medications**

At the discretion of the Investigator, the following concomitant medications may be used in accordance with the restrictions described for each treatment:

- All subjects will be provided with saline and instructions for daily intranasal saline irrigation twice a day starting from washout till Week 24/EOT.
- If a sinus infection is suspected at any time during the study, treatment with antibiotics will be allowed after a clinic visit and per Investigator's judgment.
- Subjects who have been on a stable regimen of inhaled corticosteroids for asthma for a minimum of 3 months prior to the Screening visit should remain on the same dosage throughout the study. Inhaled corticosteroid use must be limited to a stable low- or medium-dose as defined by guidelines established by the 2018 Global Initiative for Asthma Management and Prevention .
- Perennial allergic rhinitis (PAR) subjects who have been on a stable regimen of a non-sedating oral antihistamine for a minimum of 3 months prior to the Screening visit should remain on the same dosage throughout the study.

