### 8.3.1.3 Saline Irrigation Use

The ePRO will also be used to collect the frequency of daily saline irrigation by the subjects.

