14.1. DERIVATIONS

Compliance is calculated as below and will be rounded to 1 decimal place:

$$\begin{aligned} \text{Compliance per period (\%)} \\ &= \frac{\text{Number of days saline irrigation was completed during washout/treatment period}}{\text{Duration of washout/treatment period (days)}} \\ &\times 100 \end{aligned}$$

- Duration of washout period is defined as:
-

Duration of washout period (days) = washout stop date – washout start date + 1

- Duration of treatment period is the same as the duration of exposure as noted in Section 13.1 but will be converted from weeks to days (multiply by 7).

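### Washout saline compliance divides diary-recorded days by the whole washout, though the diary need only cover its last 7 days; the formula also ignores irrigation frequency

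*SAP*

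**What the plan says.** SAP Section 14 names the data source: "Compliance to daily saline irrigation will be presented descriptively by treatment group for the ITT analysis sets as collected in the ePRO". It then defines the measure: "Compliance will be presented as a percentage of the days saline irrigation was done relative to the duration of the washout and treatment periods".

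SAP Section 14.1 gives the formula, per period. The numerator is "Number of days saline irrigation was completed during washout/treatment period". The washout denominator is "Duration of washout period (days) = washout stop date – washout start date + 1". Its dates do not come from the diary: "The washout period information is collected on the Washout Period eCRF". The treatment-period denominator is the duration of exposure from SAP 13.1, converted back from weeks to days.

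Protocol 4.1.1 sets washout at 2 to 4 weeks and has irrigation start then. On the diary it says: "Beginning at least 7 days prior to Day 1 visit, subjects will record the severity of the 4 cardinal symptoms of CS". The same sentence puts daily saline use in that diary, with the same start. Footnotes l and n of the protocol's Table 1 agree on the irrigation start and the diary start.

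On the regimen, Protocol 6.4.3 provides saline and instructions for "daily intranasal saline irrigation twice a day starting from washout till Week 24/EOT". Protocol 8.3.1.3 adds: "The ePRO will also be used to collect the frequency of daily saline irrigation by the subjects".

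SAP Section 14 has no rule for washout days before the diary opens, no rule for missed entries, and no definition of a completed day. SAP 3.3, on changes from the protocol, does not mention the measure.

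**The concern.** The numerator and denominator cover different windows. A day irrigated before the diary opens is in the washout denominator but cannot be in the numerator, so it is scored as a day without irrigation. The washout figure then reflects washout length and diary start date as well as adherence. A reader comparing it with the treatment-period figure could take a measurement artefact for a change in behaviour after Day 1.

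The second gap is that frequency is collected but not used. If a day counts whenever any irrigation was done, the table cannot separate once-daily from twice-daily users.

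Saline is provided to every subject, and Protocol 2.1 describes daily irrigation as an adjunct to the most common first-line therapy. This table is the SAP's planned description of how that background care was followed, so it should measure adherence.

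**Working it through.** The documents state no compliance figure, so there is none to reproduce. The SAP 14.1 formula can be applied directly.

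**Inputs**
- Washout length W: 14 to 28 days (Protocol 4.1.1).
- Diary days before Day 1, d: at least 7 (Protocol 4.1.1 and 8.3.1.1). Seven is a minimum, and an earlier start is allowed.
- Instructed frequency: 2 per day (Protocol 6.4.3; Table 1 footnote l).
- Formula: compliance = 100 × recorded irrigation days / period duration (SAP 14.1).

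**Washout ceiling.** For a subject who irrigates every day and makes every diary entry, compliance = 100 × d / W:

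| Washout W | d = 7 | d = 10 | d = 14 | d = W |
|---|---|---|---|---|
| 14 days | 50.0% | 71.4% | 100% | 100% |
| 21 days | 33.3% | 47.6% | 66.7% | 100% |
| 28 days | 25.0% | 35.7% | 50.0% | 100% |

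If Day 1 is entered as the washout stop date, so that W is 15 or 29, and only 7 days are recorded, the ceiling is 7/15 = 46.7% or 7/29 = 24.1%.

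**Treatment-period ceiling.** The diary runs daily in this period, so the cap does not arise. Rounding exposure to 0.1 week has a trivial effect: 169 days / 7 = 24.1 weeks, 24.1 × 7 = 168.7 days, and 169 / 168.7 = 100.2%. Perfect adherence and recording can therefore give about 100% in treatment but only 25% to 50% in washout with the minimum diary.

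**If the periods were pooled.** SAP 14.1 says per period. Pooled with 169 complete treatment days, the ceiling would be (7 + 169) / (14 + 169) = 96.2% or (7 + 169) / (28 + 169) = 89.3%.

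**Frequency.** A once-daily user with a full diary over n days scores n / n = 100% if any irrigation makes a day count. Against the twice-daily instruction the score is n / (2n) = 50%.

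**After the change.** With the denominator restricted to diary-open days, the fully adherent subject with a 7-day diary scores 7 / 7 = 100% whatever the washout length.

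**The case against.** **The 7 days are a minimum.** Nothing bars opening the diary at Screening, and the understatement vanishes if it opens with washout. This stands: 50%, 33.3% and 25% are the lowest ceilings for these washout lengths, not expected values. But nothing requires the early start, and the formula has no rule for a later one.

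**A reader might infer that the SAP credits one irrigation as a full day.** It does not say so. Section 14 speaks of days on which irrigation was *done*, but the formula says *completed*, which is undefined and could be programmed as both irrigations. The ePRO items are in an appendix not available here. The protocol also calls the regimen recommended in the Synopsis and 4.1.1, but gives it as an instruction in 6.4.3. What stands is that the term is undefined and frequency is absent from the formula.

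**A reader might infer a certain false rise after Day 1, with treatment-period use overstated.** The direction is not fixed. Missed entries lower the figure in both periods, and any once-daily credit raises it in both.

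**A reader might infer a masked difference between arms.** The washout gap arises before randomization on Day 1, so it is unrelated to arm. Only the unused frequency could blur a between-arm difference, and nothing in the documents indicates one. The discharge reminders in Protocol 6.2.5 cover nose blowing and sneezing, not irrigation.

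**Counting unrecorded days as not done is a defensible conservative choice.** That is fair once the diary is open, because dropping every missed entry can flatter poor diarists. It does not justify counting days before the diary was open.

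**The measure is descriptive.** It is not an endpoint, a model covariate or a listed reason for exclusion from the per-protocol set, and it is already planned by arm and by period. All of this stands and limits the weight of the point.

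**Conclusion.** The point holds as a defect in one descriptive measure. For any subject whose diary opens after washout begins, the SAP 14.1 washout figure is capped below 100% regardless of adherence. The cap is 50%, 33.3% or 25% for the minimum 7-day diary with a washout of 14, 21 or 28 days. It varies with washout length and diary start, so washout and treatment figures should not be compared.

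The frequency gap is an under-specification: on the plain reading of *done*, a once-daily user could score 100% after half the instructed irrigations.

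The washout figures assume full adherence, complete entries and a 7-day diary. How many subjects start the diary that late is not known from the documents, so the average understatement cannot be stated. No efficacy result, hypothesis test or listed analysis-set rule depends on this table.

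**What to change.** In SAP 14.1:

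1. Start the washout denominator at the subject's first ePRO entry and end it at the washout stop date (diary-open days). Keep missed entries after that date in the denominator.
2. Report diary completion beside compliance, by period and arm, with the number of washout days before the first entry. Missed entries and late starts are then visible.
3. Define a *completed* day against the twice-daily instruction. Alternatively, if the ePRO stores a daily count, also report irrigations / (2 × diary-open days). Check the item wording first: the diary is filled in each morning, and the documents do not show whether an entry covers that day or the day before.

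The cost is rewording one formula and adding a few columns to one table. The first two changes use data already planned for collection. The count-based measure depends on how frequency is stored; Protocol 8.3.1.3 says it is collected but not in what form.
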